## **4.2 EXCLUSION CRITERIA FOR RSV-SEROPOSITIVE CHILDREN**

Potential RSV-seropositive participants who meet any of the following exclusion criteria will be excluded from participation in this study:

- 4.2.1. Born at less than 34 weeks gestation
- 4.2.2. Maternal history of positive HIV test
- 4.2.3. Evidence of chronic disease
- 4.2.4. Known or suspected impairment of immune function
- 4.2.5. Bone marrow/solid organ transplant recipient
- 4.2.6. Major congenital malformations, including congenital cleft palate or cytogenetic abnormalities
- 4.2.7. Suspected or documented developmental disorder, delay, or other developmental problem
- 4.2.8. Cardiac abnormality requiring treatment
- 4.2.9. Lung disease or reactive airway disease
- 4.2.10. More than one episode of wheezing in the first year of life
- 4.2.11. Wheezing episode or received bronchodilator therapy within the past 12 months
- 4.2.12. Wheezing episode or received bronchodilator therapy after the age of 12 months
- 4.2.13. Previous receipt of supplemental oxygen therapy in a home setting

- 4.2.14. Previous receipt of an investigational RSV vaccine
- 4.2.15. Previous receipt or planned administration of anti-RSV antibody product including ribavirin, RSV Ig or RSV mAb
- 4.2.16. Previous receipt of immunoglobulin or any antibody products within the past 6 months
- 4.2.17. Previous receipt of any other blood products within the past 6 months
- 4.2.18. Previous anaphylactic reaction
- 4.2.19. Previous vaccine-associated adverse reaction that was Grade 3 or above
- 4.2.20. Known hypersensitivity to any vaccine component
- 4.2.21. Member of a household that contains an infant who is less than 12 months of age at the date of inoculation through the 10th day after inoculation
- 4.2.22. Member of a household that, at the date of inoculation through the 10th day after inoculation, contains an immunocompromised individual including but not limited to:
  - a person who is HIV-infected
  - a person who has received chemotherapy within the 12 months prior to enrollment
  - a person receiving immunosuppressant agents
  - a person living with a solid organ or bone marrow transplant
- 4.2.23. Will attend a daycare facility that does not separate children by age and contains an infant who is < 12 months of age at the date of inoculation through the 10th day after inoculation
- 4.2.24. Receipt of any of the following prior to enrollment:
  - any inactivated vaccine or live-attenuated rotavirus vaccine within the 14 days prior, or
  - any live vaccine, other than rotavirus vaccine, within the 28 days prior, or
  - another investigational vaccine or investigational drug within 28 days prior, or
  - salicylate (aspirin) or salicylate-containing products within the past 28 days
- 4.2.25. Scheduled administration of any of the following after planned inoculation:
  - inactivated vaccine or live-attenuated rotavirus vaccine within the 14 days after, or
  - any live vaccine other than rotavirus in the 28 days after, or
  - another investigational vaccine or investigational drug in the 28 days after
- 4.2.26. Receipt of any of the following medications within 3 days of study enrollment:
  - systemic antibacterial, antiviral, antifungal, anti-parasitic, or antituberculous agents, whether for treatment or prophylaxis, or
  - intranasal medications, or
  - other prescription medications except the permitted concomitant medications listed below

Permitted concomitant medications (prescription or non-prescription) include nutritional supplements, medications for gastroesophageal reflux, eye drops, and topical medications, including (but not limited to) cutaneous (topical) steroids, topical antibiotics, and topical antifungal agents.
- 4.2.27. Any of the following events at the time of enrollment:
  - fever (temporal or rectal temperature of  $\geq 100.4^{\circ}\text{F}$ ), or
  - upper respiratory signs or symptoms (rhinorrhea, cough, or pharyngitis) or
  - nasal congestion significant enough to interfere with successful inoculation, or
  - otitis media

#### **4.3 INCLUSION CRITERIA FOR RSV-SERONEGATIVE INFANTS & CHILDREN**

Potential RSV-seronegative participants must meet all of the following inclusion criteria to be enrolled in this study:

- 4.3.1.  $\geq$  6 months of age and  $<$  25 months of age at the time of inoculation
- 4.3.2. Screening and pre-inoculation serum specimens for RSV-neutralizing antibody are obtained no more than 42 days prior to inoculation
- 4.3.3. Seronegative for RSV antibody, defined as serum RSV-neutralizing antibody titer  $<$  1:40
- 4.3.4. In good health based on review of the medical record, history, and physical examination at the time of inoculation
- 4.3.5. Received routine immunizations appropriate for age based on the ACIP Recommended Immunization Schedule for Children and Adolescents Aged 18 Years or Younger
- 4.3.6. Growing normally for age as demonstrated on a standard growth chart, AND
  - If  $<$  1 year of age: has a current height and weight above the 5th percentile for age
  - If  $\geq$  1 year of age: has a current height and weight above the 3rd percentile for age
- 4.3.7. Expected to be available for the duration of the study
- 4.3.8. Parent/guardian is willing and able to provide written informed consent

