### *Infectivity*

1. To determine the peak titer of vaccine virus shed and duration of virus shedding by each participant
2. To assess the proportion of vaccinated participants infected with study vaccine (If < 70% of RSV-seronegative vaccinees are infected with vaccine virus, the study product will be considered over-attenuated.)

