## **3 STUDY DESIGN**

The study will be double-blind, randomized, and placebo-controlled. Participants in groups 1 and 2 will be block-randomized in groups of 3 at a ratio of 2:1 to receive vaccine or placebo, respectively. The vaccine will be evaluated in a stepwise fashion beginning with RSV-seropositive children (Group 1) and proceeding sequentially in RSV-seronegative children (Group 2). For the purpose of this study, RSV-seropositive is defined as having a serum neutralizing antibody titer of  $\geq 1:40$ , and RSV-seronegative is defined as having a serum neutralizing antibody titer of  $< 1:40$ . This definition has been used in previous evaluations of live-attenuated RSV vaccines (11, 24, 35). In these previous studies, live-attenuated RSV vaccines were highly restricted in replication and poorly immunogenic in children with titers  $\geq 1:40$  but were far less restricted in replication and highly immunogenic in children with titers  $< 1:40$ . These data suggest that this neutralizing antibody cutoff can distinguish effectively between RSV-experienced and RSV-naïve children.

The study will proceed to group 2 if there are not more than 2 vaccine-associated solicited AEs and no vaccine-associated LRIs in RSV-seropositive children. If 3 or more RSV-seropositive children have respiratory or febrile illness that coincides with shedding of  $> 10^{2.5}$  PFU of vaccine virus as detected by culture, then we will enroll an additional 15 RSV-seropositive children to continue evaluating the safety, infectivity, and immunogenicity of the vaccine virus.

Enrollment occurs at the time of inoculation with study product, Day 0, and will occur between April 1 and October 31 to avoid the time during which wt RSV typically circulates in the community ([Appendix V](#), Figure 6). Accrual will stop prior to November 1.

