## **4.1 INCLUSION CRITERIA FOR RSV-SEROPOSITIVE CHILDREN**

Potential RSV-seropositive participants must meet all of the following inclusion criteria to be enrolled in this study:

- 4.1.1.  $\geq$  12 months of age and  $<$  60 months of age at the time of inoculation
- 4.1.2. Screening serum specimen for RSV-neutralizing antibody is obtained within the calendar year of inoculation
- 4.1.3. Seropositive for RSV antibody, defined as serum RSV-neutralizing antibody titer  $\geq$  1:40
- 4.1.4. Pre-inoculation serum sample for RSV-neutralizing antibody specimen is obtained no more than 56 days prior to inoculation
- 4.1.5. In good health based on review of the medical record, history, and physical examination at the time of inoculation
- 4.1.6. Received routine immunizations appropriate for age based on the Advisory Committee on Immunization Practices (ACIP) Recommended Immunization Schedule for Children and Adolescents Aged 18 Years or Younger
- 4.1.7. Growing normally for age as demonstrated on a standard growth chart and has a current height and weight above the 3rd percentile for age
- 4.1.8. Expected to be available for the duration of the study
- 4.1.9. Parent/guardian is willing and able to provide written informed consent

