## 6.6.2 Weekly Contact for Surveillance during the RSV Season

Based on previous data regarding the seasonality of RSV in the Baltimore, MD, area ([Appendix IV](#), Figure 6), surveillance for RSV-associated disease will be conducted between November 1 and March 31 during the first RSV season following receipt of study product. For some RSV-seronegative participants, surveillance during the first RSV season may overlap with the Acute and/or Post-Acute study phases. In this case, all evaluations required for each of the relevant phases of the study will be conducted.

During the first RSV season following receipt of study product, participants enrolled in this study will be monitored for symptomatic, medically attended, RSV-like illnesses listed below via weekly telephone or email communication or an in-person visit. (Rhinorrhea and cough need not meet the [Appendix IV](#) criteria if they are documented by the health care provider):

- Medically attended fever
- Medically attended URI
- Medically attended otitis media
- Medically attended LRI

An Illness Visit will be scheduled within 3 days of study staff notification of any of these events (Section [6.8](#)).

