## **9.2 OUTCOME MEASURES**

### **9.2.1 Primary Outcome Measures**

*Safety: Types and grades of study product-related:*

- Solicited AEs as defined in Appendix IV from Study Days 0-10 for RSV-seropositive and Study Days 0-28 for RSV-seronegative participants
- Unsolicited AEs from Study Days 0-10 for RSV-seropositive and Study Days 0-28 for RSV-seronegative participants
- SAE (Section 8.1.2) from Study Days 0-28 for RSV-seropositive and Study Days 0-56 for RSV-seronegative participants

*Infectivity:*

- Infection with RSV as defined as
  - 1) vaccine virus identified in a nasal wash from Study Days 0-10 for RSV-seropositive and Study Days 0-28 for RSV-seronegative (a binary outcome based on nasal washes done throughout the study period; Day 0 nasal wash will be counted as baseline); or
  - 2)  $\geq 4$ -fold rise in RSV neutralizing antibody titer from Study Days 0-28 for RSV-seropositive and Study Days 0-56 for RSV-seronegative subjects
- Peak titer of vaccine virus shed from Study Days 0-10 for RSV-seropositive and Study Days 0-28 for RSV-seronegative subjects
- Duration of virus shedding in nasal washes as determined by a) culture and b) RT-PCR from Study Days 0-10 for RSV-seropositive and Study Days 0-28 for RSV-seronegative subjects

*Immunogenicity:*

- $\geq 4$ -fold rise in RSV-neutralizing antibody titer from study entry to Study Day 28 for RSV-seropositive and from study entry to Study Day 56 for RSV-seronegative subjects
- $\geq 4$ -fold rise in IgG antibody responses to RSV F glycoprotein (ELISA) from study entry to Study Day 28 for RSV-seropositive and from study entry and Study Day 56 for RSV-seronegative subjects

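### Group 2's eligibility and baseline serum may be drawn inside the RSV season, so a cleared wild-type infection before dosing can count as vaccine infection; in the first enrolment year this touches at most 14 of 214 inoculation dates

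*Combined protocol and SAP*

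**What the plan says.** Section 3 states that inoculation "will occur between April 1 and October 31 to avoid the time during which wt RSV typically circulates in the community". Section 6.6.2 sets the season: "surveillance for RSV-associated disease will be conducted between November 1 and March 31 during the first RSV season following receipt of study product".

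The rules for the blood draw count back from inoculation and do not mention the season:

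- **Group 2 (4.3.2):** "Screening and pre-inoculation serum specimens for RSV-neutralizing antibody are obtained no more than 42 days prior to inoculation". The same serum sets seronegativity and the baseline titer.
- **Group 1 (4.1.4):** "Pre-inoculation serum sample for RSV-neutralizing antibody specimen is obtained no more than 56 days prior to inoculation". The eligibility serum may be older; 4.1.2 requires that "Screening serum specimen for RSV-neutralizing antibody is obtained within the calendar year of inoculation".
- **Day 0 (Table 4):** blood is taken only if the screening volume fell short. Section 6.4.1 calls for Group 2 rescreening only once the 42 days are exceeded.

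Section 9.2.1 defines infection as vaccine virus in a nasal wash or a fourfold or greater "rise in RSV neutralizing antibody titer from Study Days 0-28 for RSV-seropositive and Study Days 0-56 for RSV-seronegative subjects". Section 6.10.3 shows that the first serum of that pair may precede Day 0 by up to 42 days in Group 2 and 56 in Group 1. Section 2.1 attaches a decision: "If < 70% of RSV-seronegative vaccinees are infected with vaccine virus, the study product will be considered over-attenuated".

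**The concern.** The April 1 start is the plan's protection against mixing wild-type infection with vaccine effect. It covers the dose but not the specimen that classifies the child and anchors the titer comparison.

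Suppose a Group 2 child is seronegative at an in-season draw, has a mild wild-type infection, and is well on Day 0. That child is no longer RSV-naive when dosed. The rise to Day 56 includes the response to the natural infection, and the serological limb cannot tell the two apart. Section 6.10.3 itself reads a fourfold rise across the season as wild-type infection. The virus-recovery limb is not the problem, because it requires vaccine virus.

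At stake is the Group 2 infected proportion, where a false positive makes the vaccine look less over-attenuated than it is. The same child may also shed less vaccine virus: Section 3 reports that earlier live-attenuated RSV vaccines were highly restricted in children with titers of at least 1:40. The errors therefore need not all run one way.

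**Working it through.** The plan gives no figure for this risk, and its stated sample sizes and power are not in question.

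**Inputs from the documents.** Season November 1 to March 31. Inoculation April 1 to October 31, which is 214 days. Serum limit 42 days (Group 2) or 56 days (Group 1 baseline). Group 2 opens only after Group 1 has been assessed for lower respiratory illness through Day 28 (Protocol Summary). Group 2 has 14 to 20 vaccinees.

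**Group 2, first enrolment year.** Suppose all of Group 1 is dosed on April 1.
- Earliest Group 2 dose: April 1 + 28 days = April 29.
- Oldest serum for that dose: April 29 − 42 days = March 18, so March 18 to 31 gives 14 in-season days.
- Last dose that can rest on an in-season serum: March 31 + 42 days = May 12.
- Affected dates: April 29 to May 12 = 14; 14/214 = 6.5%. A later Group 1 finish shrinks this further.

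**Group 2, later enrolment year.** Nothing confines enrolment to one year, and Section 4.8 lets placebo recipients re-enrol after their surveillance season.
- Oldest serum: April 1 − 42 days = February 18 (February 19 in a leap year).
- Affected dates: April 1 to May 12 = 42; 42/214 = 19.6%.

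**Group 1 baseline.** April 1 − 56 days = February 4. Affected dates run to March 31 + 56 days = May 26, so 56/214 = 26.2%.

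**Effect of one child.** 1/20 = 5 points; 1/14 = 7.1 points. For example, 13/20 (65%) becomes 14/20 (70%). This holds only if the child would not otherwise meet either limb.

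**Risk in the gap (assumption, not in the documents).** Take a monthly in-season risk m of 5% to 15% in naive children, with risk over d days = 1 − (1 − m)^(d/30), and every child using the full 42-day limit.

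| Case | In-season days d | Risk per child |
|---|---|---|
| First year, worst date | 14 | 2.4% to 7.3% |
| First year, mean over the 14 dates | 7.5 | 1.3% to 4.0% |
| Later year, worst date | 42 | 6.9% to 20.3% |
| Later year, mean over the 42 dates | 21.5 | 3.6% to 11.0% |

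With 20 vaccinees and even accrual:
- First year (April 29 to October 31 = 186 days): 20 × 14/186 = 1.5 vaccinees in the window. Expected gap infections are 1.5 × 1.3% to 4.0% = 0.02 to 0.06.
- Later year: 20 × 42/214 = 3.9 vaccinees. Expected gap infections are 3.9 × 3.6% to 11.0% = 0.14 to 0.43.
- Accrual concentrated in spring would raise both.

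**Ceiling on the 70% rule.** Suppose every vaccinee carried gap risk q, independently of a true vaccine infection rate of 60%. The counted rate is then 0.60 + 0.40q. The chance of reaching 70% is the binomial probability of at least 14 of 20, or at least 10 of 14.

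| q | n = 20 | n = 14 |
|---|---|---|
| 0 | 0.250 | 0.279 |
| 2% | 0.274 | 0.300 |
| 5% | 0.312 | 0.333 |
| 10% | 0.380 | 0.392 |

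Only children dosed in the window carry the risk, so the true effect lies below these rows.

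**The case against.** The strongest reply is that the plan already filters most such children and that few could be affected.

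- **Clinical filters.** Wheezing or bronchodilator use in the past 12 months excludes (4.4.12), health is judged at inoculation (4.3.4), and fever or respiratory signs defer dosing (6.4.1). This stands for noticeable or current illness. It does not stand for a mild infection that has cleared.
- **Day 0 nasal wash.** It can detect a child still shedding. It misses a cleared infection, and no rule says what follows a positive result.
- **Placebo arm.** Infection before dosing falls on both randomized arms, so the one-sided Fisher test of fourfold response (9.5.1) has its own control. This stands for that test. The 70% rule subtracts no placebo rate.
- **Line listings.** Section 9.5.1 lists individual shedding and paired titers, so serology-only infections can be found afterwards. True, but no analysis of them is planned. They can be common: Section 1.2.1 reports 7% culture shedding but 53% neutralizing responses for the related ΔNS2/Δ1313/I1314L candidate at 10^5 PFU.
- **Sequence.** The wait for Group 1 stands in full and sets the first-year limit.

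A reader might infer that a fifth of Group 2 enrolment dates are exposed, with sera from mid-February. The documents support that only if Group 2 enrols in a later year. A reader might also infer that Group 1 is equally compromised. Group 1 children cannot enter as seronegative, and the rule for proceeding to Group 2 uses adverse events, lower respiratory illness, and illness with shedding. Fourfold rise plays no part in it. The only Group 1 effect is that a natural boost may be reported as a vaccine response.

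**Conclusion.** The gap is real for Group 2. Its eligibility and baseline serum can date from the plan's own RSV season, no routine Day 0 titer closes the interval, and a fourfold rise alone counts as infection toward a rule applied to vaccinees only.

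It is narrow. The first-year limit assumes that Group 1 is fully dosed on April 1, and the wider limit requires Group 2 enrolment in a later year. On the assumed 5% to 15% monthly risk and even accrual, the expected number of gap infections among 20 vaccinees is well below one in either case. The point matters because the group is small and the threshold fixed: one child not otherwise infected can turn 65% into 70%. It does not follow that every such child shifts the result, since one who also sheds vaccine virus changes nothing. Nor does it undermine the seronegative definition for most enrolment dates.

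**What to change.** 1. In 4.3.2, 6.2 and Table 3, require the Group 2 screening and pre-inoculation draw on or after April 1 of the inoculation year, within the existing 42-day limit. Apply the same date to the Group 1 baseline draw in 4.1.4, within its 56 days. Do this by scheduling the single planned draw then.
2. Do not rely on a routine second draw without checking volume. Section 6.10.3 caps blood at 20 mL for Group 2 through season 1 and 10 mL for Group 1. The schedules already use 5 + 5 + 5 + 5 = 20 mL and 5 + 5 = 10 mL. Children dosed April 29 to May 12 reach Day 56 between June 24 and July 7, so that visit cannot double as the October pre-season visit. Any repeat draw must fit within the caps, or the caps must be reconciled.
3. In 9.5.1, add a sensitivity analysis of the infected and fourfold-response proportions excluding participants whose baseline serum predates April 1. Report serology-only infections separately by arm.

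**Cost.** The first inoculations each year slip by the serology turnaround, which the documents do not give. The analysis uses data already collected. One gap remains: a late-March infection that has not yet seroconverted on April 1 could still be missed.

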#### **4.4 EXCLUSION CRITERIA FOR RSV-SERONEGATIVE INFANTS & CHILDREN**

Potential RSV-seronegative participants who meet any of the following criteria will be excluded from this study:

- 4.4.1. Born at less than 34 weeks gestation
- 4.4.2. Born at less than 37 weeks gestation, and at the date of inoculation less than 1 year of age
- 4.4.3. Maternal history of a positive HIV test
- 4.4.4. Evidence of chronic disease
- 4.4.5. Known or suspected infection or impairment of immunological functions
- 4.4.6. Bone marrow/solid organ transplant recipient
- 4.4.7. Major congenital malformations, including congenital cleft palate or cytogenetic abnormalities
- 4.4.8. Suspected or documented developmental disorder, delay, or other developmental problem
- 4.4.9. Cardiac abnormality requiring treatment
- 4.4.10. Lung disease or reactive airway disease
- 4.4.11. More than one episode of wheezing in the first year of life
- 4.4.12. Wheezing episode or received bronchodilator therapy within the past 12 months
- 4.4.13. Wheezing episode or received bronchodilator therapy after the age of 12 months
- 4.4.14. Previous receipt of supplemental oxygen therapy in a home setting

- 4.4.15. Previous receipt of an investigational RSV vaccine
- 4.4.16. Previous receipt or planned administration of anti-RSV antibody product including ribavirin, RSV Ig, or RSV mAb
- 4.4.17. Previous receipt of immunoglobulin or any antibody products within the past 6 months
- 4.4.18. Previous receipt of any blood products within the past 6 months
- 4.4.19. Previous anaphylactic reaction
- 4.4.20. Previous vaccine-associated adverse reaction that was Grade 3 or above
- 4.4.21. Known hypersensitivity to any study product component
- 4.4.22. Member of a household that contains an infant who is less than 6 months of age at the date of inoculation through the 28th day after inoculation
- 4.4.23. Member of a household that, at the date of inoculation through the 28th day after inoculation, contains an immunocompromised individual including but not limited to:
  - a person who is HIV-infected
  - a person who has cancer and has received chemotherapy within the 12 months prior to enrollment
  - a person living with a solid organ or bone marrow transplant
- 4.4.24. Attends a daycare facility that does not separate children by age and contains an infant < 6 months of age at the date of inoculation through the 28th day after inoculation
- 4.4.25. Receipt of any of the following prior to enrollment:
  - any inactivated vaccine or live-attenuated rotavirus vaccine within the 14 days prior, or
  - any live vaccine, other than rotavirus vaccine, within the 28 days prior, or
  - another investigational vaccine or investigational drug within 28 days prior, or
  - salicylate (aspirin) or salicylate-containing products within the past 28 days
- 4.4.26. Scheduled administration of any of the following after planned inoculation
  - inactivated vaccine or live-attenuated rotavirus vaccine within the 14 days after, or
  - any live vaccine other than rotavirus in the 28 days after, or
  - another investigational vaccine or investigational drug in the 56 days after
- 4.4.27. Receipt of any of the following medications within 3 days of study enrollment:
  - systemic antibacterial, antiviral, antifungal, anti-parasitic, or antituberculous agents, whether for treatment or prophylaxis, or
  - intranasal medications, or
  - other prescription medications except the permitted concomitant medications listed below

Permitted concomitant medications (prescription or non-prescription) include nutritional supplements, medications for gastroesophageal reflux, eye drops, and topical medications, including (but not limited to) cutaneous (topical) steroids, topical antibiotics, and topical antifungal agents.
- 4.4.28. Any of the following events at the time of enrollment:
  - fever (temporal or rectal temperature of  $\geq 100.4^{\circ}\text{F}$ ), or
  - upper respiratory signs or symptoms (rhinorrhea, cough, or pharyngitis) or
  - nasal congestion significant enough to interfere with successful inoculation, or
  - otitis media

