## 4 STUDY POPULATION

Approximately 15 RSV-seropositive children  $\geq$  12 months to  $<$  60 months of age will be enrolled; 10 will receive a single dose of  $10^{5.7}$  PFU of vaccine and 5 will receive a single dose of placebo. Subsequently, 21 to 30 RSV-seronegative infants and children  $\geq$  6 months to  $<$  25 months of age will be enrolled in the study and will receive a single dose of either  $10^{5.0}$  PFU of vaccine or placebo in a 2:1 ratio. These numbers were chosen based upon experience with phase I evaluation of other live-attenuated respiratory virus candidate vaccines ([11,23,25](#)) and statistical considerations (Section 9).

Placebo recipients are needed in pediatric studies to distinguish the background respiratory and febrile illnesses that occur in infants and children from those attributable to study vaccine. These numbers were chosen based upon experience with phase I evaluation of other live-attenuated respiratory virus candidate vaccines ([11,23,25](#)) and statistical considerations (Section 9).

Infants and children will be selected for participation according to the described study-specific co-enrollment considerations; the recruitment, screening, and enrollment process; and participant retention and withdrawal or termination.

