#### **4.7 CO-ENROLLMENT CONSIDERATIONS**

Co-enrollment to an investigational vaccine or investigational drug study is not allowed during the Acute Phase or Post-Acute Phase of this study. After the Post-Acute Phase, co-enrollment may be considered at the discretion of the principal investigator (PI).

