#### **4.9 RECRUITMENT PROCESS**

CIR research staff will recruit participants from pediatric practices and clinics in the greater Baltimore/Washington area. Upon referral by the participants' primary care provider or the provider's staff, CIR staff will approach parents/guardians, present them with IRB-approved informational brochures, and obtain contact information. Study staff will contact interested parents/guardians to elaborate upon the details and requirements of the study.

CIR research staff may also recruit participants through mailing IRB-approved documents to children of local pediatric practices and clinics, and to households in local zip codes containing age-appropriate children. In addition, CIR staff may recruit participants through group gatherings such as health fairs and by posting IRB-approved recruitment materials.

If parents/guardians are interested in having their child participate and the child meets the minimum inclusion and exclusion criteria, then the study staff will schedule a screening visit to determine the child's eligibility.

After the first year of RSV surveillance is completed, the parents/guardians of children enrolled in group 2 will be invited to have their children participate in a second year of RSV surveillance. Participation is optional, and separate consent will be obtained for participation in this portion of the study.

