### **6.3 RANDOMIZATION**

Randomization numbers will be assigned by the unblinded laboratory vaccine dispenser and will be forwarded to the Data Safety Monitoring Board (DSMB) Executive Secretary. Unblinded laboratory personnel will label the vaccine syringes with the study virus vaccine name, PI initials, study number, subject's randomization number, preparer and vaccine verifier's initials and expiration date and time. The vaccine administrator and verifier will initial the label and place the label in the subject's study chart. The vaccination time will be documented on the vaccine administration record (VAR). All syringes will be disposed of by the study staff following the enrollment visit. A copy of the VAR will be sent to the laboratory.

A copy of the randomization code will be retained by the unblinded dispenser in the laboratory where the vaccine is prepared. Without the PI's written request to unblind, the randomization code will not be released to the clinical staff until the acute monitoring phase is complete for each subject within the randomization group. Pediatric subjects will be block-randomized in groups of 3 (2 vaccinees and 1 placebo recipient per block); this allows for maintenance of the blind during each subject's acute monitoring phase but also provides early information regarding safety, which is appropriate and common practice for phase 1 respiratory virus vaccine studies (11,23,25). Detailed procedures for randomization and unblinding will be placed in the laboratory study binder.

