## 6.5 STUDY PHASES

Refer to [Figures 1](#) and [2](#) for timelines of study visits. The Acute Phase begins with inoculation and ends at midnight on the 10th day after inoculation for RSV-seropositive participants, and at midnight on the 28th day after inoculation for RSV-seronegative participants. During the Acute Phase of the study, a study healthcare professional will be available by telephone 24 hours a day for consultation with parent/guardian regarding any illnesses that may occur.

Study personnel will have daily contact with RSV-seropositive participants' parents/guardians for the first 10 days after inoculation, and for the RSV-seronegative participants during the first 28 days after inoculation. This 28-day period is consistent with the duration of shedding of live-attenuated respiratory virus vaccines in RSV-seronegative participants ([28](#), [37-39](#)).

On non-visit days, study staff will contact the parent/guardian and will record the parent/guardian-provided temperatures and signs of illness. Participants with illness may have additional visits to assess the illness (Section [6.8](#), Illness Visit).

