**Table 25: Percent of Participants Experiencing LRI or AEs with Exact 90% CI**

[figure not shown]
N	% LRI or AEs	90% CI
10	0%	0% -- 26%
20	0%	0% -- 14%
10	10%	1% -- 39%
20	10%	2% -- 28%
10	20%	4% -- 51%
20	20%	7% -- 40%
10	30%	9% -- 61%
20	30%	14% -- 51%

Group sample sizes of 20 in the vaccinated group and 10 in the placebo group would achieve 80% power to detect a difference between the group proportions of about 0.45. The test statistic used is the one-sided Fisher's exact test. The alpha level of the test was targeted at 0.05. Table 26 presents examples of true group differences which can be detected with 80% power, and Figure 5 graphically shows power curves for 90% power, 80% power, and 70% power given the sample sizes.

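### Section 4.4 lets two seronegative children of one household be in the Acute Phase together in different arms, so a placebo child could acquire vaccine virus from a sibling

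*Combined protocol and SAP*

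**What the plan says.** The Group 2 contact criteria (4.4.22 to 4.4.24) run from inoculation through Day 28. They exclude a "Member of a household that contains an infant who is less than 6 months of age at the date of inoculation", a child living with an immunocompromised person, and a child in certain mixed-age daycare. Section 6.5 gives the reason for the length of the window: "This 28-day period is consistent with the duration of shedding of live-attenuated respiratory virus vaccines in RSV-seronegative participants".

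The places where a household rule might otherwise stand do not contain one:

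- Section 4.3 admits children from 6 to under 25 months, a range that can include twins or closely spaced siblings.
- Section 4.7 concerns other studies: "Co-enrollment to an investigational vaccine or investigational drug study is not allowed during the Acute Phase or Post-Acute Phase of this study".
- Section 4.9 includes mailings "to households in local zip codes containing age-appropriate children", with no limit on children per household.
- Sections 3 and 6.3 randomise each child individually, 2:1 in blocks of 3, with no household rule.
- Section 9.5.1 does not say how vaccine virus found in a placebo recipient is analysed.

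Section 4 states what the placebo arm is for: "Placebo recipients are needed in pediatric studies to distinguish the background respiratory and febrile illnesses" from those due to the vaccine.

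**The concern.** The contact criteria treat spread of shed virus to close contacts as possible, but they do not cover the contact who matters most for the comparison, namely another participant in the same home. A seronegative sibling on placebo is as susceptible as the children the vaccine is meant to infect.

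If that sibling acquires vaccine virus, Section 9.2.1 counts the child as infected (virus in a nasal wash, or a 4-fold neutralising rise) and possibly as an antibody responder. Any resulting illness is counted as background. Each of these moves the placebo arm toward the vaccine arm. With 7 to 10 placebo children planned in Group 2, a single child is visible in the results.

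**Working it through.** **Inputs from the documents.** 20 vaccine and 10 placebo children (lower end of the range: 14 and 7), one-sided Fisher's exact test at 0.05, and the pairs of rates in Table 26 (Section 9.3.1). Section 9.3.1 states: "Group sample sizes of 20 in the vaccinated group and 10 in the placebo group would achieve 80% power".

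**Assumptions, not in the documents.** The number of placebo children living with an enrolled vaccinee (one in the main calculation) and the probability q that virus passes to that child (0.1 to 1).

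**1. Reproduce the plan's figure.** Exact enumeration of the test over two binomials gives power 0.806, 0.797, 0.795, 0.801 and 0.797 for the five rows of Table 26. The stated 80% is confirmed.

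**2. Chance that two siblings are in different arms.**

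- Same block of 3 (two vaccine, one placebo): both on vaccine has probability (2/3)(1/2) = 1/3, and both on placebo is impossible, so different arms = 1 − 1/3 = 2/3.
- Different blocks: 2 × (2/3) × (1/3) = 4/9.

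**3. Weight of one child.** 1/10 = 10 points of the placebo proportion; 1/7 = 14 points.

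**4. Power with one exposed placebo child.** The exposed child responds with probability pp + (1 − pp) × q × pv, where pp and pv are the placebo and vaccine rates. The other placebo children respond at pp. For pp = 0.05, pv = 0.52 and q = 1 this is 0.05 + 0.95 × 0.52 = 0.544. The expected placebo rate becomes (9 × 0.05 + 0.544)/10 = 0.099, and the difference falls from 0.47 to 0.42.

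| Rates (placebo, vaccine) and size | No exposure | q = 0.1 | q = 0.25 | q = 0.5 | q = 1 |
|---|---|---|---|---|---|
| 0.05, 0.52; 20 vs 10 | 0.81 | 0.79 | 0.77 | 0.73 | 0.65 |
| 0.05, 0.52; 14 vs 7 | 0.53 | 0.51 | 0.49 | 0.44 | 0.36 |
| 0.05, 0.80; 20 vs 10 | 0.998 | 0.997 | 0.996 | 0.994 | 0.990 |
| 0.05, 0.80; 14 vs 7 | 0.97 | 0.96 | 0.95 | 0.93 | 0.89 |

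The two vaccine rates are close to the neutralising responses that Section 1.2.1 reports for the predecessor candidate at its two dose levels, 53% and 80%. The 5% placebo rate is taken from Table 26.

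**5. One enrolled pair, before its arms are known.** Power = 0.806 − d × (0.806 − power with exposure), where d is the probability from step 2. The mildest case (d = 4/9, q = 0.1) is 0.806 − 0.444 × 0.015 = 0.80. The most severe (d = 2/3, q = 1) is 0.806 − 0.667 × 0.153 = 0.70.

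**The case against.** The other side has four good arguments.

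**No evidence of frequency.** The documents report no transmission of vaccine virus and no sibling enrolment. Both children must be 6 to under 25 months, with a titre below 1:40 within 42 days of inoculation, and the preterm exclusions remove some twins. Mailing to households is one recruitment route among several and does not show that siblings enrol together. This stands: the expected effect may be zero.

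**The size is easily overstated.** A reader might infer that one contaminated child cuts power to 51–65%. Those figures arise in the first four rows of Table 26 if one placebo child is fixed as a certain responder, which assumes that a split pair enrols, that transmission is certain and that response is certain. The fifth row gives 72% even then. An exposed child can hardly be assumed to respond more often than a vaccinee, so the table above is the fairer range.

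**It can be seen.** A reader might infer that the damage cannot be examined afterwards. Every Group 2 child has nasal washes for virus on Days 0, 3, 5, 7, 10, 12, 14, 17 and 28, and shedding and antibody titres are line-listed (Sections 6.5.2.1 and 9.5.1). A contaminated placebo child would usually be identified, and a sensitivity analysis is simple. What remains is that dropping the child departs from the randomised comparison, so prevention is cleaner.

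**Much of the trial is untouched.** A reader might infer that every contrast and decision is affected. The under-70% infection criterion in Section 2.1 uses vaccinees only, the stopping criteria in Section 8.3 concern vaccine recipients, and Section 9.1.2 describes the study as exploratory. Nor do the documents support extending the point to Group 1: Section 3 reports that earlier candidates replicated poorly at titres of 1:40 or above, and Section 1.2.1 reports no shedding of the predecessor in seropositive children.

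**Conclusion.** The gap is real and confined to Group 2. Nothing in the documents keeps two susceptible children of one household from overlapping in the Acute Phase in different arms; the manual of procedures was not available to check. If it happens and virus passes, the comparisons of shedding, antibody and illness are biased toward no difference.

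The size depends on two unknowns. With one exposed placebo child in the 0.05 versus 0.52 row at 20 versus 10, power goes from 0.81 to 0.79–0.65 for q from 0.1 to 1. It stays at about 0.99 or above with an 80% vaccine response at that size, and is unchanged if no siblings overlap. The smaller design of 14 versus 7 is more sensitive. This is an inexpensive precaution rather than an error in the plan.

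**What to change.** Add one exclusion to Section 4.4: a child living with another participant whose Acute Phase would overlap with the child's own. In effect, one child per household is in the Acute Phase at a time.

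Add one sentence to Section 9.5.1: a placebo recipient in whom vaccine virus is found is analysed as randomised, with a sensitivity analysis excluding that child.

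Assigning siblings to the same arm would be an alternative, but the analysis would then have to account for the clustering.

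The cost is two short text changes and an occasional sibling deferred or lost, which could slow accrual slightly within the April to October enrolment window.
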